
**11. Provide a BRIEF DESCRIPTION of how the estimated number of study subjects needed for this research was determined**

- *If this is a quantitative study provide the method of determining sample size estimates.*
- *If multiple studies are planned provide a power analysis or justification for each one.*

To determine the number of subjects needed for this study, we conducted a power analysis based on our preliminary data of increase in pulse size ratio and pulse time delay after the 10-minute fatigue test in two different sample populations of MS patients with INO. Based on a large effect size of 0.93, we found that we will need a sample size of 9 patients to reach a power of 0.80 (alpha 0.05) for the first outcome measure (pulse size ratio). Based on a moderately large effect size of 0.63, we found that we will need a sample size of 17 patients to reach a power of 0.80 (alpha 0.05) for the second outcome measure (pulse time delay). Because only one out of three patients showed clinically significant changes of pulse size ratio and pulse time delay after dalfampridine, while changes were subclinical in the other two patients, we were not able to provide a power analysis for the expected effects of dalfampridine in our trial. However, we found that for a clinically meaningful effect size of 0.5, with alpha of 0.05, we will need a sample size of 27 patients to yield a power of 0.85 [Norman et al., 2000]. Thus we aim at recruiting, studying and treating 30 patients.

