**10. Describe the means of analyzing the data and evaluating the results.**

- *State the anticipated methods to be used for analysis and interpretation of the data.*
- *The methods must compliment the design of the study and the nature of the data which is being collected.*

This study investigates horizontal binocular conjugacy and ocular motor fatigue in MS patients with INO and the effects of treatment (dalfampridine) while eye movements are recorded during a 10-minute saccadic fatigue test. Patients will undergo clinical eye movement examination, visual performance assessment including reading acuity and speed, gait assessment, assessment of symptomatic fatigue, disability arising from visual dysfunction as well as quality of life, using available self-administered questionnaires and scales, and eye movement recording, before and after treatment. The treatment portion of the study will be conducted following a randomized, placebo-controlled, double-blind, crossover trial design, which will include a period of wash out of at least two weeks between treatment with dalfampridine and placebo. A minimum of 2 weeks is necessary to ensure wash out, however a washout period longer than 2 weeks will not confound the study results. There will be a total of 4 evaluations: at baseline, after washout, and after treatment with both dalfampridine and placebo. Subject participation will last an estimated 10-14 weeks. We anticipate most subjects will participate for 10 weeks, however due to unforeseen circumstances a subject may be unable to keep a scheduled appointment lengthening the overall time of their participation. In order to test our hypotheses, we use the following outcome measures, at time of each evaluation. A. Eye movement assessment: changes in binocular horizontal conjugacy at baseline and following the saccadic fatigue test using 1) abducting/adducting eye ratio for saccadic peak velocity (pulse size ratio); 2) time difference in occurrence of peak acceleration in the adducting vs. the abducting eye (pulse time delay). These measures of conjugacy of horizontal saccades are applied to data collected continuously throughout the fatigue test. B. Symptomatic fatigue assessment using 1) Fatigue Severity Scale (FSS); 2) Modified Fatigue Impact Scale (MFIS); C. Visual function assessment using 1) MNREAD acuity charts for reading acuity and speed; 2) King-Devick test for saccades performance; D. Gait assessment using 1) 25-foot Walk Test; 2) 6-minute Walk Test. E. Visual disability and quality of life assessment using 1) NEI-VFQ-25 and NOS; 2) MS Quality of Life Inventory. Standard statistical measures, such as paired dependent t-test, will be employed to determine significance of our results.

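### The stated power of 0.85 with 27 patients at effect size 0.5 does not reproduce with the paired t-test: it is 0.81 one-sided or 0.71 two-sided, and item 11 gives neither sidedness nor SD

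*Combined protocol and SAP*

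**What the plan says.** The form's instruction for item 11 reads: "If this is a quantitative study provide the method of determining sample size estimates". The answer contains three calculations.

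- **Pulse size ratio, change over the fatigue test.** Effect size 0.93 from preliminary data: "we found that we will need a sample size of 9 patients to reach a power of 0.80 (alpha 0.05").
- **Pulse time delay, change over the fatigue test.** Effect size 0.63 from preliminary data: "we will need a sample size of 17 patients to reach a power of 0.80 (alpha 0.05").
- **Dalfampridine effect.** Because only one of three pilot patients changed to a clinically significant degree, "we were not able to provide a power analysis for the expected effects of dalfampridine in our trial". The plan turns instead to a benchmark it calls clinically meaningful: "effect size of 0.5, with alpha of 0.05, we will need a sample size of 27 patients to yield a power of 0.85". This sentence carries a literature citation. The target follows: "Thus we aim at recruiting, studying and treating 30 patients".

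On analysis, item 10 says: "Standard statistical measures, such as paired dependent t-test, will be employed to determine significance of our results". No other test is named. Neither item states whether tests are one- or two-sided, which SD standardises the effect sizes, or a within-patient correlation.

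**The concern.** Effect size, alpha, sample size and power are tied together once the test and the SD are fixed, so any three determine the fourth. For the paired t-test, the quoted set does not hold together on either sidedness.

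The plan says it could not power the drug effect from its own data. The 0.5 benchmark is therefore the only quantitative support for the randomised comparison, and the target of 30 is drawn from it. If the power is lower than stated, a null result says less than readers will assume. With sidedness missing, they cannot tell whether the shortfall is trivial or about ten percentage points.

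**Working it through.** **Inputs.** From item 11: effect sizes 0.93, 0.63 and 0.5; n = 9, 17 and 27; target 30; alpha 0.05; stated power 0.80, 0.80 and 0.85. From item 10: paired t-test, crossover design. Not given, so both options are run: one- or two-sided testing, and the SD behind the effect size.

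**Formula.** With d on the SD of the paired differences, the test statistic follows a noncentral t with n − 1 degrees of freedom and noncentrality δ = d√n. One-sided power is P(T > t₀.₉₅). Two-sided power is P(|T| > t₀.₉₇₅).

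**Step 1: the plan's three figures.** For the benchmark, δ = 0.5 × √27 = 2.598 with 26 degrees of freedom, and the critical values are 1.706 one-sided and 2.056 two-sided.

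| d | n | Stated power | One-sided | Two-sided |
|---|---|---|---|---|
| 0.93 | 9 | 0.80 | 0.816 | 0.687 |
| 0.63 | 17 | 0.80 | 0.7997 | 0.684 |
| 0.5 | 27 | 0.85 | 0.812 | 0.706 |
| 0.5 | 30 | – | 0.848 | 0.754 |

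The first two rows match a one-sided test at power 0.80. For 0.63 exactly as printed the strict minimum is 18, but 17 suffices for 0.634, which also prints as 0.63. The third row matches on neither sidedness.

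**Step 2: patients needed.**

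| d | Power | One-sided n | Two-sided n |
|---|---|---|---|
| 0.5 | 0.80 | 27 | 34 |
| 0.5 | 0.85 | 31 | 38 |
| 0.93 | 0.80 | 9 | 12 |
| 0.63 | 0.80 | 18 (17 to rounding) | 22 |

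So 27 is the one-sided number for 0.80, and 0.85 is to rounding the one-sided power at 30. Either could explain the printed pair, but that is inference.

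**Step 3: other routes to 0.85 at n = 27, d = 0.5 (one-sided / two-sided).**

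- Normal approximation: 0.830 / 0.738; 0.85 needs 29 / 36.
- Crossover t-test with n − 2 degrees of freedom: 0.811 / 0.704.
- Wilcoxon signed-rank, assuming relative efficiency 0.955: about 0.79 / 0.68.
- Two independent groups of 27: 0.58 / 0.45.
- Effect size on a single-measurement SD, with assumed within-patient correlation ρ. The paired effect size is then d / √(2(1 − ρ)):

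| ρ (assumed) | Paired effect size | One-sided | Two-sided |
|---|---|---|---|
| 0.3 | 0.423 | 0.69 | 0.56 |
| 0.5 | 0.500 | 0.81 | 0.71 |
| 0.7 | 0.645 | 0.95 | 0.90 |

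Power 0.85 is reached at ρ ≈ 0.56 one-sided or 0.65 two-sided. If the same ρ applied to the other two calculations, they would need 8 and 16 patients, or 9 and 16, rather than 9 and 17.

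- Repeated-measures F-test over the four evaluations, assuming f = 0.25 and ρ = 0.5. The noncentrality is f² × n × 4 / (1 − ρ) = 0.0625 × 27 × 4 / 0.5 = 13.5 on 3 and 78 degrees of freedom, giving 0.87.

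**Step 4: what the planned numbers detect.** The smallest effect with power 0.85 is 0.53 one-sided or 0.60 two-sided at n = 27, and 0.50 or 0.57 at n = 30. With 30 completers, two-sided power of 0.80 needs an effect of 0.53.

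**The case against.** The best defence is that the fault is missing inputs, not a wrong number. Item 10 offers the paired t-test only as an example. Item 11 cites a source that is not in the documents, and the 9 and 17 concern a different comparison, change over the fatigue test, so they need not share a convention with the drug benchmark.

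A single conventional reading also comes close to all three figures: two-sided, effect sizes on a single-measurement SD, ρ = 0.65. Then 0.93 needs 9 patients, an effect of 0.626 (printed as 0.63) needs 17, and 27 patients give 0.848 at effect size 0.5. A four-evaluation F-test can also exceed 0.85, and item 10 does schedule that many: "There will be a total of 4 evaluations: at baseline, after washout, and after treatment with both dalfampridine and placebo". On the one-sided reading, 30 completers deliver the stated power anyway.

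Much of this stands. The alternatives cannot be excluded, and the one-sided shortfall is small. But the ρ = 0.65 route needs a correlation given nowhere and rounding in two places at once: 0.63 taken as about 0.626, and 0.848 read as 0.85 when 28 patients are strictly needed. The F-test inputs are equally unstated, and with two measurements instead of four its power falls to 0.706. A citation does not supply the missing inputs. Every rescue therefore relies on something item 11 was asked to provide and did not.

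**Conclusion.** The concern holds and should be fixed. For the one test the plan names, with the effect size on the SD of paired differences, power at 27 patients is 0.81 one-sided or 0.71 two-sided, not 0.85.

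The practical size depends on the sidedness. One-sided, the chance of missing an effect of 0.5 is 19% with 27 patients and 15% if all 30 complete, so the error nearly disappears at the planned enrolment. Two-sided, it is 29% and 25%, against the 15% implied.

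The arithmetic is certain given the test and SD. Why 0.85 was printed is not, and a different SD or test could restore it. The fatigue-test calculations are safe, since 30 patients exceed even the two-sided needs of 12 and 22.

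**What to change.** Keep enrolment at 30. In item 11, name the test, say whether 0.05 is one- or two-sided, say which SD defines the effect sizes, and restate the power to match:

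- **One-sided, SD of paired differences:** *For an effect size of 0.5, power is 0.81 with 27 completers and 0.85 with 30.* The 9 and 17 can stay.
- **Two-sided, SD of paired differences:** *For an effect size of 0.5, power is 0.71 with 27 completers and 0.75 with 30; 30 completers give power 0.80 for an effect size of 0.53.* The fatigue-test figures become 12 and 22.
- **Single-measurement SD or another test:** state the assumed within-patient correlation and any other inputs, and recompute all three figures.

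The cost is wording in item 11, with no added patients and no change of design. The stated power is unchanged at 30 completers if the test is one-sided, and about 10 points lower if it is two-sided.

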**12. The research involves the following procedures conducted by and for what purpose:**

PROCEDURE	PERFORMED BY:		PROCEDURE IS:	
	Research Staff	LSCDVAMC Clinical or Support Staff	Standard of Care*	For Research Purposes Only**
Audiotaping / Videotaping Attach VA Form 10-3203 REQUIRED ONLY FOR IN-PATIENT AND OUT-PATIENT SUBJECTS				
Biopsy				
Blood collection				
Chart review – prospective				
Chart review – retrospective				
Review of existing data ( ex: registry, Database , etc.)				
X-ray or Ionizing radiation exposure				
Clinical Tests				
Device implantation				
Drug administration				
EEG, EKG , ECG...etc				
Gene therapy, Genetic analysis				

PROCEDURE	PERFORMED BY:		PROCEDURE IS:	
	Research Staff	LSCDVAMC Clinical or Support Staff	Standard of Care*	For Research Purposes Only**
Pregnancy/Breastfeeding Screening				
Interview, Questionnaire, Diary, Survey (please attach)				
Stool collection, Urine collection, or any Non-surgical Specimen collection				
Surgical procedure or Specimen removal during surgery				
Tissue banking (complete Section 12)				
Use of pre-existing tissues/specimens				
Other (list): Eye Movement Recording				

- \*Standard of care procedures are procedures performed in the course of normal medical care.
- \*\*Research Procedures are performed for the purposes of this research alone.

**13. Please describe the research design and all study related procedures.**

- *Describe **ALL PROCEDURES ASSOCIATED WITH THIS RESEARCH**. This includes standard of care and research procedures.*
- *For complex studies please include diagrams and tables. Be sure to describe when each procedure will be performed. Be sure to provide information for **each cohort, including normal controls**).*

Patients cohorts (n=30).

Enrollment. [name] will be responsible for enrolling all patients for the study, whether he is the primary neurologist caring for the patients or whether they are being referred to him for possible enrollment in the study.

All patients will undergo neurological evaluation (medical history, clinical neurological examination, including eye movements exam, and blood work for renal function panel) prior to selection to establish whether or not they meet the study inclusion criteria. Possible female participants will also undergo a urine pregnancy test. [name] will evaluate all patients as above.

Randomization and masking. Patients will be randomized to study drug or placebo for the first 4 weeks of treatment then, after a wash-out period of at least 2 weeks, they will cross-over to placebo and study drug respectively for another 4 weeks of treatment. Randomization process will be carried out by a VA research pharmacist. The patient, the PI, and all personnel and investigators involved in the study will be masked to treatment assignment. To avoid the possibility of a patient running out of the study drug/placebo at the time of the

2nd or 4th visit, for example in case of visit cancellation due to unforeseeable circumstances, the study drug/placebo will be sent out for 5 weeks. However, every effort will be made to schedule patients as close as possible to the 4-week mark for the 2nd and 4th visit. Additionally, all unused study medications will be returned by the subject to the laboratory at the 2nd and 4th visits.

Procedures to be performed at Evaluation 1 ,2 ,3 ,4.

Video tape of subjects' eye movements.

**Eye Movement Recording.** Eye movements will be recorded using the EyeLink II system, (SR Research Ltd.). Subjects will sit in a 110-ft-lb vestibular chair (CNC Engineering), with head restrained, during all the experimental paradigms, and will follow a visual stimulus (a red laser spot) projected onto tangent screen. The EyeLink signal from each eye will be calibrated. We will obtain a baseline monocular and binocular viewing recording of eye movements then will perform the 10-minute saccadic fatigue test as previously described [Matta et al, 2009]. Patients will make horizontal saccades in response to 20-degree jumps, at 0.5 Hz across the midline (i.e., 1 saccade per second), of the visual target (laser spot).

At evaluations 2 and 4, patients will hold the am dose (dalfampridine or placebo), will undergo baseline eye movement recording, then will be recorded again 3 hours after taking their dose in the same session.

Visual function assessment using MNREAD acuity charts for reading acuity and speed and the King-Devick test for saccades performance. [name] will carry out these assessments.

Symptomatic fatigue assessment using self-administered questionnaires: the Fatigue Severity Scale (FSS) and the Modified Fatigue Impact Scale (MFIS).

Gait assessment using the 25-foot Walk Test and the 6-minute Walk Test. [name] will carry out these assessments.

Visual disability and quality of life assessment using the following self-administered scales: NEI-VFQ-25 and NOS; and the MS Quality of Life Inventory.

Renal function panel (serum) at baseline, to be repeated after 4 weeks and at the end of the trial. Phlebotomy will be performed by a lab technician in the blood work laboratory located in the first floor of the LSDVAMC.

Normal controls cohort (n=20).

**Enrollment.** [name] will be responsible for enrolling all age-matched normal controls for the study, including possibly residents, house staff and employees of the LSDVAMC and Case.

All controls will undergo clinical evaluation of vision and eye movements to confirm they have normal visual and ocular motor functions.

**Eye Movement Recording (one session only).** Eye movements will be recorded using the EyeLink II system, (SR Research Ltd.). Normal controls will sit in a 110-ft-lb vestibular chair (CNC Engineering), with head restrained, during all the experimental paradigms, and will follow a visual stimulus (a red laser spot) projected onto tangent screen. The EyeLink signal from each eye will be calibrated. We will obtain a baseline monocular and binocular viewing recording of eye movements then will perform the 10-minute saccadic fatigue test as previously described [Matta et al, 2009]. Normal controls will make horizontal saccades in response to 20-degree jumps, at 0.5 Hz across the midline (i.e., 1 saccade per second), of the visual target (laser spot).

The table below summarizes the randomized, placebo-controlled, double-blind, crossover trial design, which will include a period of wash-out of at least two weeks between treatment with dalfampridine and placebo. In the event the washout period lasts longer than 2 weeks or a subject has difficulty keeping one of the study visits and needs to reschedule, subject participation would be greater than 10 weeks (estimated 10-14 weeks of participation).

[figure not shown]

Table. Flow diagram summarizing study design. Following enrollment and randomization subjects will undergo a total of 4 evaluations, each one consisting in: eye movement recording, symptomatic fatigue assessment, visual function assessment, gait assessment, visual disability and quality of life assessment. Renal function panel (serum) will be performed at baseline, to be repeated after 4 weeks and at the end of the trial. See text for details.

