**31. By role, (PI, Coordinator, etc.) who will assess for eligibility and how will this be accomplished?**

Eligibility will be assessed by the PI, [name], who will conduct formal neurological, neuro-ophthalmologic and neurotological clinical examinations. Then subjects will be selected based on the inclusion criteria specified above.

**32. Are any subjects excluded on the basis of race, ethnic group, understanding of English, socioeconomic status, education, gender, or pregnancy?**

- *Note: It is appropriate to indicate that you do not anticipate encountering potential subjects who do not speak English based on the population to be studied*

No       Yes - (provide justification): Non-English speaking individuals who cannot give informed consent will be excluded because they will be unable to follow the directions required to conduct the experiments. We will exclude individuals who are pregnant or likely to become pregnant because the study involves the use of a category C medication such as dalfampridine.

N/A Chart/data review

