**40. Describe all procedures that minimize risks, please include study and standard of care procedures:**

We will not enroll subjects in which AMYRA is contraindicated: history of seizure, moderate or severe renal impairment, history of hypersensitivity to AMPYRA or similar compounds. To minimize possible side effects, subjects will be taking the FDA-recommended dose of AMPYRA (10 mg tablet twice daily), with doses taken approximately 12 hours apart and only taken whole. Subjects will be advised not to take double or extra doses if a dose is missed.

Since AMPYRA can cause side effects, especially seizures, in subjects with abnormal renal function, this will be checked through standard blood work at baseline, after 4 weeks and at the end of the study.

We will keep all eye movement recordings under 30 minutes to minimize possible discomfort.

If subjects do not wish to answer a question in a questionnaire, they may skip it and go to the next question.

To ensure confidentiality of patient's records, we will keep all records on a password-protected computer in Room BC 300c in the Daroff-Dell'Osso Ocular Motility Laboratory. This computer has an encryption firewall. Paper records will also be kept in a locked cabinet in Room BC 300c; the keys to the room and cabinet will be retained by [name]. Each patient will be assigned a number based on the hour and date of their study. The key to the numbers/patients will be stored in [name] password-protected computer and in the memories of each patient and [name]. At the end of the study, all data will be stored on a password-protected CD, kept in [name] locked cabinet and will be retained indefinitely.

**41. Describe alternative procedures or course of treatment, if any, which might be advantageous to the subject. State if no alternatives exist or if this is not a treatment study.**

AMPYRA is potentially available to subjects outside of the research study with the FDA-approved indication for gait impairment. Because of the nature of this research the only alternative is to not participate in this study. Currently, there are no other approved treatment/drugs for the treatment of INO.

**Minimal Risk:** Minimal risk means that the risks of harm anticipated in the proposed research are not greater, considering probability and magnitude, than those ordinarily encountered in daily life or during the performance of routine physical or psychological examinations or tests.

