## Section 14 – Other

97. Please describe any other study procedures not referenced in the previous sections:

Not applicable

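### No repeat pregnancy test is described between entry and period 2, although women given placebo first nominally start dalfampridine 6 or more weeks into the trial

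*Combined protocol and SAP*

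**What the plan says.** Item 13 describes the neurological examination and blood work done before patients are selected, and adds: "Possible female participants will also undergo a urine pregnancy test". The form's instruction for that item is "Be sure to describe when each procedure will be performed". The item then lists the procedures for Evaluations 1 to 4. The figure caption summarises them: "Following enrollment and randomization subjects will undergo a total of 4 evaluations, each one consisting in: eye movement recording", followed by the fatigue, visual, gait and quality-of-life assessments. The renal panel is given its own schedule: baseline, after 4 weeks, and end of trial. No pregnancy test appears in either list.

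The table in item 12 ticks "Pregnancy/Breastfeeding Screening" as a research procedure done by clinical or support staff, without timing. Item 32 gives the reason for the exclusion: "We will exclude individuals who are pregnant or likely to become pregnant because the study involves the use of a category C medication". Item 30 lists pregnancy as an exclusion criterion, and item 65 makes it a ground for removal.

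Each treatment period lasts 4 weeks, with a washout of at least 2 weeks between them (items 10 and 13). On total duration, item 10 says "We anticipate most subjects will participate for 10 weeks", and items 10 and 22 give a range of 10 to 14 weeks.

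**The concern.** The described test is tied to trial entry, but the risk it guards against begins with the first dalfampridine dose. In a parallel trial, or in the drug-first sequence here, the two are close together. In the placebo-first sequence they are separated by a full treatment period and a washout. A woman who conceives in that interval and does not yet know it could start the drug with every described step followed. That is the exposure the trial's own exclusion is meant to prevent. What is at stake is participant safety; efficacy estimates, power and type I error are not involved.

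**Working it through.** **Inputs.** Period 1: 4 weeks. Washout: at least 2 weeks. Period 2: 4 weeks. Tablets supplied per period: 5 weeks (all item 13). Participation: 10 to 14 weeks (items 10 and 22). The interval from the entry test to the start of period 1 is not stated, so times below run from the start of period 1. The true gap from the test is longer by that interval.

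**Step 1: reproduce the plan's duration.** Period 1 + minimum washout + period 2 = 4 + 2 + 4 = 10 weeks. This matches item 10, so the minimum washout is the expected case.

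**Step 2: time to the first dalfampridine dose.**
- Drug-first: 0 weeks.
- Placebo-first, nominal minimum: period 1 + washout = 4 + 2 = 6 weeks.
- Placebo-first, upper bound: maximum participation − period 2 = 14 − 4 = 10 weeks. This requires all the delay to fall before period 2.

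**Step 3: time from the last described test to the last dalfampridine dose** (screening interval again left out).

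| Sequence | As described | With a repeat at Evaluation 3 |
|---|---|---|
| Drug-first | 4 weeks (5 if the whole supply is used) | unchanged; the drug period is over by then |
| Placebo-first | 4 + 2 + 4 = 10 weeks, up to 14 | 4 weeks (5 if the whole supply is used) |

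In the expected case the repeat shortens the placebo-first interval by 10 − 4 = 6 weeks and brings it level with drug-first. These are intervals since a test, not time on drug: planned exposure is 4 weeks in either sequence.

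**Step 4: look for a re-check in the text.** Item 13's enrollment paragraph has one test. Its Evaluation 1 to 4 procedures have none, and the figure caption has none. The renal panel shows that the authors do schedule repeat safety tests where they intend them. Tests described: 1. Repeats described: 0.

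**Step 5: ask whether the other safeguards act at the right time.** Item 32's exclusion is a judgement made at entry. Item 65 acts once a pregnancy is known, but no means of detecting one is described. Neither establishes status at the start of period 2.

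**The case against.** Most of the case against concerns evidence and weight, and a good part of it stands.

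- **The record is incomplete.** The flow diagram and consent pages were not available. Consent wording is a natural place for contraception advice or a duty to report pregnancy, so a reader who infers that the trial has no such provisions goes beyond the documents. The figure is a weaker reservation, because its caption lists the visit content and repeats only the renal panel.
- **A reader might infer that placebo-first women start the drug with no pregnancy check at all.** That is wrong: the entry test precedes every dose in both sequences. What is absent is a described re-check between entry and period 2.
- **A reader might also take silence elsewhere as confirmation.** Item 40 asks "Describe all procedures that minimize risks, please include study and standard of care procedures" and its answer does not mention pregnancy testing. But it also omits the entry test, which item 13 does describe, so its silence shows nothing about a repeat. Item 97 asks "Please describe any other study procedures not referenced in the previous sections" and is answered as not applicable. Pregnancy screening had already been named in item 12, so that answer is uninformative too. The point rests on item 13 and its caption.
- **The risk is already reduced.** With pregnant women and those judged likely to conceive excluded, what remains is unrecognised conception among women judged unlikely to conceive. This stands, and it is why the point is minor.
- **No text sets a testing frequency, and the drug is marketed and given at its recommended dose.** Also true. But the trial itself chose to exclude pregnancy because of this drug, and the described steps do not carry that choice through to the placebo-first sequence.
- **The 6 weeks is nominal.** Visit 2 is targeted near week 4, so a visit a few days early would shorten the gap slightly.

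**Conclusion.** The point holds as a small safety improvement. The visible procedures describe one urine pregnancy test before selection and no repeat before period 2. Placebo-first women nominally take their first dalfampridine dose 6 or more weeks after period 1 starts, and up to about 10 weeks within the 14-week range. The entry exclusion and removal rule reduce the risk but do not check status at that moment.

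This rests on the planned period lengths being kept and on the visible text alone. If the consent form or flow figure already contains a repeat test, item 13 only needs to say so. The documents give neither the number of women who could become pregnant nor a conception rate, so no expected count is offered; it is probably small. No endpoint, estimate or sample-size figure is affected.

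**What to change.** In item 13, add the same urine pregnancy test at Evaluation 3, after washout, for all women who could become pregnant, in both sequences. Require a negative result before the first period 2 dose. Item 13 has tablets sent to patients, and the documents do not say when the second supply goes out. So either hold dispensing until the result is known, or tell these women not to start until they have been given it.

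Testing both sequences keeps the masking. In drug-first women the repeat comes after their dalfampridine period, but masking is not its only use: it also detects a pregnancy that would trigger removal under item 65.

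The cost is one extra urine test per relevant woman at an existing visit, by staff who already do the screening. It also needs a small dispensing or instruction step, and matching consent wording if the form does not already cover it. The test will miss very early pregnancies and does not cover conception during active treatment, so it narrows the gap without removing it.
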